Some participants may also have co-occurring conditions which would prevent them from participation in the imaging arm of the study (claustrophobia; presence of metal in the body). These participants will be enrolled in the study but will not complete imaging procedures. A chart review of PIRATE participants to date indicates that approximately 20% of veterans enrolled in PIRATE may have such exclusionary criteria: roughly 17% report pacemaker or other implanted metal objects or devices incompatible with MR scanning. Thus, the participant sample used to address the neuroanatomical hypotheses proposed under Specific Aim 1 may be smaller than the sample contributing data the other proposed analyses. Under the worst case scenario of no overlap between these imaging-related exclusionary criteria and those described in the preceding paragraph, we expect to obtain a sample size of 40 participants (50 minus 20%) to conduct the proposed imaging-related analyses. As described in section C.3.1.3 below, this sample size should be sufficient to detect the relationships relevant to the neuroanatomical hypotheses.

C.2 Procedures

The schedule of procedures for participants enrolling in the study is summarized in the flowchart in Figure 4. Participants enrolling in the research study will receive a single pre-treatment structural MRI and a battery of cognitive assessments at program entry (see section C.2.3 below). They will also have their performance on standardized measures of naming and other language functions assessed repeatedly throughout the protocol (see section C.2.2 below), and they will receive an intensive dose of a treatment (SFA) designed to target lexical-semantic processes (see section C.2.1 below). Participants' performance on treated and untreated lexical items will be probed three times weekly, to assess acquisition and generalization and to decide when participants will move to a novel set of treatment exemplars.

Half the participants will be randomly assigned to a delayed-treatment condition. The purpose of this condition is to provide an additional measure of experimental control, to ensure that any observed improvements are not due simply to the social contact afforded by the residential component of the treatment program. Previous work [7] has found that simple exposure or engagement in the absence of specific therapy

[figure not shown]

Figure 4: Testing and treatment procedures for study participants

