Treatment will be conducted five days a week (Monday through Friday) across two daily 120-minute intervals, one morning session and one afternoon session, for a total of 4 hours of treatment per day and 20 hours per week. A 20-minute break will be provided within each 120-minute treatment interval and a 120 minute break will be provided between each 120-minute treatment interval. Time in treatment will be recorded in daily logs, as will the number of exposures to each training exemplar, the number of treatment trials, and the number of features (both novel and recurring) generated for each item on a given treatment trial. In addition, participants will be engaged in planned social and recreational activities on the weekends, such as visits to

local sites and events (like a baseball game). These activities will not target or specifically stimulate language function or the skills trained in therapy.

As indicated above, half the participants will be enrolled in treatment immediately upon their arrival at VAPHS, and half will be entered into the delayed-treatment condition. Participants assigned to the delayed-treatment condition will arrive one week prior to treatment initiation. During this week, they will be in residence at the HJ Heinz campus and engage in non-language recreational activities in 2 two-hour sessions per day (the same schedule as will be followed during treatment). These activities will be led by a study staff member experienced in working with stroke survivors. The morning session will consist of recreational activities regularly conducted at the H.J. Heinz campus, listed in Table 6 below:

Billiards	Recreational Hall, H.J. Heinz campus
Physical exercise	Gym, H.J. Heinz campus
Ceramics, other visual arts	Art Studio, H.J. Heinz campus
Puzzles and board games	Recreational Hall, H.J. Heinz campus

Table 6. Non-language-focused recreational activities for participants enrolled in delayed-treatment condition

The afternoon session will consist of either complementary activities drawn from Table 6 or off-site visits to local destinations. While these sessions will afford multiple social contacts and interactions, typical of structured recreational programs, they will not target specific speech and language behaviors. Participants randomized to the delayed treatment group will receive probes (naming and PNT and other assessments [CAT, discourse measures]) on the same schedule as the no-delay group.

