For all naming probes, nonword repetition control probes, and the PNT, initial dichotomous scoring will be completed online by the study staff administering the stimuli. This online scoring will be used for the purposes of establishing inter-rater reliability. Primary scoring of each of these variables will be completed by a different member of the study staff from the audio-recorded responses. Prior to primary scoring, the filenames of audio recordings will be scrambled with respect to administration date so that the scorer will be blind to the measurement point. Inter-rater reliability between primary scoring and online scoring will be assessed for each participant by percentage point-to-point agreement and across participants by intraclass correlation coefficient.

In addition to the probes described above, we will also collect data on two standardized assessments of language performance to examine the generalized effects of intensive lexical-semantic naming treatment. These include the Comprehensive Aphasia Test^[99] and the connected speech task described by Nicholas and Brookshire^[100]. The language battery of the CAT is comprised of several subtests designed to assess both word and sentence level performance in the areas of auditory and reading comprehension, repetition, naming, spoken and written picture description, oral reading and writing. T-scores based upon a well-described

normative sample of adults with aphasia (n = 146) may be derived for each of the eight modalities to provide a profile of the measured impairment, and a mean modality T-score is computed to provide an overall estimate of the severity of the impairment. We will use modality T-scores to examine changes in reading, writing and comprehension performance in response to treatment.

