The first analysis will evaluate whether the social contact associated with PIRATE participation results in improved performance on study measures, independent of any actual aphasia treatment. We will use a multivariate mixed model to test whether there are any differences between the immediate-treatment and delayed-treatment groups at the initiation of treatment, and whether there is any group-by-time interaction suggesting a positive effect of the delayed treatment week. The dependent variables will include performance on treated and untreated naming probes and PNT short forms.

If this analysis finds no significant differences between the groups, it will suggest that any observed treatment gains can be attributed to the SFA treatment rather than general effects of the social contact associated with PIRATE. In this case, the two groups will be collapsed for further analysis. In the unexpected event that this analysis finds a significant difference favoring the delayed treatment condition, it will suggest that observed treatment gains should be attributed to the combination of SFA and the socialization inherent in a residential treatment program, rather than to SFA alone. In this case, we will use the data to estimate the size of the socialization effect and statistically control for it in subsequent analyses, where possible.

C.3.1 Psycholinguistic, cognitive, and neuroanatomical predictors of treatment response

The primary dependent variable for analyses relevant to Specific Aim 1 will be the proportion of correctly-named treated stimuli at study exit (post-treatment), minus the proportion of correctly-named treated stimuli at study entry (pre-treatment). This difference score provides the simplest measure of naming treatment response. Supplementary analyses may be carried out using a related dependent variable, the percentage of possible naming improvement^[10]. This is a derived measure which divides the simple pre-post difference score

by the difference between pre-treatment naming performance and ceiling performance (100% accuracy minus observed pre-treatment accuracy). This measure helps correct for observed differences in baseline accuracy.

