In order to evaluate whether the study treatment is associated with broad gains in communicative function beyond confrontation naming, we will analyze data obtained from the Comprehensive Aphasia Test (CAT) and the connected speech samples described above in section C.2.2. Specifically, we will conduct a multivariate linear mixed model analysis with measurement point (initial evaluation, program entry, program exit, follow-up) as a fixed factor, subjects as a random factor, and the following dependent variables: CAT reading, writing, auditory comprehension and mean modality T-scores, and, from the connected speech samples, the percentage of correct information units (%CIUs) and the number of correct information units per minute (CIUs/min). We anticipate that there will be significant increases in the CAT auditory comprehension and mean modality T-scores and in the two connected speech measures (%CIUs, CIUs/min) from program entry to program exit, showing generalized improvement in communicative function. We have no strong predictions regarding the generalized effects of SFA on reading and writing abilities as measured by the CAT.

C.4 Timetable

This proposal is for a four-year research project. Based on an October 1, 2012 start date, recruitment of participants should begin with the November 2012 PIRATE session of 2012. Enrollment will take place continuously through September 2016, with dissemination of results continuing through December 2016.

C.5 Investigators

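### The delayed-arm check on social contact names only naming outcomes, while the CAT and connected-speech analysis in C.3.3 has no arm term

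*Combined protocol and SAP*

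**What the plan says.** **Purpose of the delayed arm.** Section C.2 says that half the participants are randomised to delayed treatment to "ensure that any observed improvements are not due simply to the social contact afforded by the residential component of the treatment program". That aim is not limited to naming.

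**What happens in the contact week.** Section C.2.1 has these participants arrive one week before treatment and attend recreational sessions on the treatment timetable. It adds: "While these sessions will afford multiple social contacts and interactions, typical of structured recreational programs, they will not target specific speech and language behaviors". They "will receive probes (naming and PNT and other assessments [CAT, discourse measures]) on the same schedule as the no-delay group".

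**The arm comparison.** Section C.3 specifies one analysis that uses the arm, a mixed model testing for a group difference at the start of treatment and a group-by-time interaction. "The dependent variables will include performance on treated and untreated naming probes and PNT short forms". If nothing is significant, gains are credited to SFA rather than to contact and the groups are collapsed. If the delayed arm does better, the effect is to be estimated and controlled for later where possible.

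**The broader outcomes.** Section C.2.2 collects the CAT and connected speech to "examine the generalized effects of intensive lexical-semantic naming treatment". Section C.3.3 uses them to "evaluate whether the study treatment is associated with broad gains in communicative function beyond confrontation naming", and analyses them with "measurement point (initial evaluation, program entry, program exit, follow-up) as a fixed factor, subjects as a random factor". It expects increases in auditory comprehension, mean modality T-score, %CIUs and CIUs/min "from program entry to program exit, showing generalized improvement in communicative function".

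**The concern.** The protocol itself names residential contact as a rival explanation and randomises participants to address it. The specified comparison then covers picture naming only. Its result decides whether gains are credited to SFA and whether the arms are merged, and C.3.3 follows with a pooled before-and-after model. A null result on naming would thus support a causal reading of CAT and connected-speech gains that were never compared by arm.

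At stake is the claim that SFA generalises beyond naming. As planned, that claim would rest on an uncontrolled rise during a residential stay, with the randomised data that bear on the rival explanation left unused for these outcomes.

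**Working it through.** The plan states no power, SD, effect size or alpha for the arm comparison or for C.3.3, so there is no figure to reproduce. The check has three parts.

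**1. Outcomes set against analyses**

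| Outcome | Measured in delayed arm (C.2.1) | Named in arm comparison (C.3) | Arm term in its own model |
|---|---|---|---|
| Naming probes, PNT forms | Yes | Yes | Yes (C.3 group and group-by-time) |
| CAT, connected speech | Yes | No | No (C.3.3) |

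The C.3.3 model does contain an untreated interval, from initial evaluation to program entry. Under C.2 the initial evaluation is a two-day visit 4-6 weeks before entry. That interval speaks to time and practice. It cannot show the effect of residence in the immediate arm, whose participants are not yet resident.

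**2. Where the contact week falls**

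- C.2 has candidates return at program entry and then live on site for 4 weeks, or 5 in the delayed condition. On this reading entry is at arrival, and the contact week lies between entry and exit.
- C.2.1 puts the delayed arm's CAT and discourse assessments on the immediate arm's schedule, without saying whether that schedule is anchored to arrival or to treatment start.
- C.3 compares the arms at treatment initiation, which needs data from after the contact week.
- C.3.2 places time points 2 through 6 from program entry to program exit and treats them as the four treatment weeks. Five points make four weekly intervals, which fits entry at treatment start. On this reading the contact week lies between initial evaluation and entry.

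C.3 and C.3.2 concern naming and PNT, but C.3.3 uses the same visit labels. The documents do not settle which reading applies. Either way, half the pooled sample has a contact week inside one of the C.3.3 intervals, and a model without arm cannot isolate it.

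**3. What an arm comparison could show**

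Inputs: 50 completers expected (C.1) and half randomised to delay (C.2), so 25 per arm. Assumptions not in the documents: two-sided alpha of 0.05, and effects in SD units of the change score.

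- Smallest arm difference with 80% power: (1.960 + 0.842) × √(2/25) = 2.802 × 0.283 = 0.79 SD. The t distribution gives 0.81 SD.
- 95% CI half-width: t(0.975, 48) × √(2/25) = 2.011 × 0.283 = 0.57 SD. For an assumed SD of change of 3 to 5 T-score points, that is 1.7 to 2.8 points.
- Pooled before-and-after test, n = 50: 80% power at 0.40 SD.

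| True effect (SD) | Power, pooled test, n = 50 | Power, arm comparison, 25 v 25 |
|---|---|---|
| 0.2 | 0.28 | 0.11 |
| 0.3 | 0.55 | 0.18 |
| 0.4 | 0.79 | 0.28 |
| 0.5 | 0.93 | 0.41 |
| 0.8 | >0.99 | 0.79 |

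Detecting 0.4 SD between arms with 80% power would need 2 × (2.802/0.4)² = 98.1, so 99 per arm.

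If SFA had no effect on an outcome but the stay raised it by 0.4 SD, the pooled test would be significant with power of about 0.79. The arm comparison sees one week of contact. If that week carries no more than the effect of the whole stay, its power would be about 0.28 at most.

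**The case against.** **Contact may not be a strong rival here.** C.2 cites earlier work in which exposure or engagement without therapy did not explain gains in communicative function, which is this very domain. B.1 drops the program's group conversation activities from the study as a potential confound, and C.2.1 says the outings do not target language. This stands against a stronger reading that a reader might infer, that connected speech and the CAT are the outcomes most open to social contact. No section ranks outcomes that way. The point needs less: C.2 itself wants the question settled more conclusively in this study, and the contact sessions do involve social interaction.

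**The C.3 outcome list is not worded as exhaustive, and later adjustment is allowed.** True, and C.3.3 is a later analysis. But the adjustment is triggered by a comparison that names only naming and PNT outcomes, and it applies only where possible. Nothing commits the plan to comparing arms on the CAT or connected speech.

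**There is a comparator.** A reader might infer that these outcomes have none. That is true of the planned analysis and false of the data, since the randomised delayed arm has both measures.

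**The comparison would be weak.** Correct, as the working shows. It argues against a pass/fail test, but not against reporting an estimate with its interval.

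**These are additional analyses, framed as association.** Also correct, and it limits the weight of the point: no Aim 1 or Aim 2 hypothesis test is affected. Even so, C.2.2 and C.3.3 also speak of generalized effects of the treatment.

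**Conclusion.** The point holds as an omission in the analysis plan. The control for contact is specified for naming and PNT outcomes only, its null result is allowed to license attribution to SFA, and C.3.3 has no arm term. A pooled rise on the CAT or in connected speech cannot then be separated from residential contact.

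The size of any contact effect on these outcomes cannot be taken from the documents. It is tempting to count 4 resident weeks in one arm and 5 in the other and to say that the pooled gain carries an average of 4.5 weeks of contact. That requires entry at arrival and a constant weekly effect. The first is unresolved and the second is not stated anywhere.

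Adding the arm comparison would not exclude a contact effect. At 25 per arm it has 80% power only for about 0.8 SD, and one contact week cannot show the effect of a full stay. These figures rest on 50 completers, equal allocation and a two-sided alpha of 0.05.

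**What to change.** 1. State whether the delayed arm's program-entry CAT and connected-speech assessment falls at arrival or after the contact week, and reconcile C.2, C.2.1, C.3 and C.3.2 on this.
2. Add arm and arm by measurement point to the C.3.3 model.
3. For each CAT and connected-speech outcome, report the arm difference in change, with a 95% CI, over the interval that contains the contact week: entry to exit if entry is at arrival, initial evaluation to entry if it comes after the contact week.
4. Say that a null arm comparison on naming and PNT does not carry over to these outcomes, and word the C.3.3 conclusion as the result of SFA delivered in a residential program.

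Cost: two model terms, one clarification of timing and a sentence on interpretation. No participants or assessments are added. The price is an imprecise estimate and a softer claim.

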There was significant improvement from initial evaluation to program entry ($F[1,40] = 6.042$, $MSE = 0.014$, $p = 0.018$, $\eta_p^2 = 0.131$) and relatively greater improvement between program entry and program exit ($F[1,40] = 53.168$, $MSE = 0.013$, $p < 0.001$, $\eta_p^2 = 0.571$). The observed pattern of minimal change across the baseline interval coupled with significant improvement across the treatment interval supports the effectiveness of PIRATE in treating aphasia. In addition, these changes on this broad measure of language performance likely underestimate the magnitude of treatment-related changes in the proposed research. The PICA samples communicative functioning at a broad level, encompassing performance not only in targeted domains (such as naming)

[figure not shown]

Figure 1. Mean PICA z-scores for n=35 patients with complete data available at three assessment points. Error bars indicate +/- 1 standard error.

but also in domains not targeted in therapy, which are unlikely to show improvement. The language performance assessments to be used in the proposed research measure performance on naming behaviors which are the object of treatment, rather than a broad index of both treated and untreated behaviors. Consequently, we may expect that the intensive delivery schedule followed in PIRATE and in the proposed research will result in even larger gains on study measures than those described here.

B.1.3 Analysis of Preliminary Data 2: Dose-Response Relationship

As noted above, the first six PIRATE sessions were three weeks in length, and the remaining sessions have been four weeks in length. Comparison of outcomes between groups receiving 3 versus 4 weeks of treatment permitted us to estimate the marginal benefit of an additional week of intensive aphasia treatment in terms of a broad performance-based outcome. To derive these estimates, we conducted ANCOVAs on the PICA overall z-scores, with the post-treatment scores as the dependent variable, treatment group (3-week vs. 4-week) as the independent variable, and pre-treatment scores collected at program entry as the covariate.

For the PICA, data at program entry and program exit were available for 15 veterans who received three weeks of treatment and 27 veterans who received four weeks. The demographic and clinical characteristics of each group are presented in Table 2.

	3-Week Group (n=15)	4-Week Group (n=27)
Months Post Onset at Program Entry, Median (IQR)	19 (38)	21 (31)

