administrations. This criterion is necessary to permit selection of the necessary treatment and generalization probe items as described below, and will minimize ceiling effects on the naming probes. Fourth, in order to avoid enrolling into the study participants who have profound naming impairments and are therefore unlikely to benefit from the study treatment (e.g., patients with global aphasia and/or verbal output limited to recurrent stereotypy), all participants must obtain a CAT Naming modality T-score greater than or equal to 40. Finally, we will exclude from participation potential participants with severe motor speech disorder (i.e., apraxia of speech and/or dysarthria). Motor speech diagnosis and severity judgments will be made by study investigators with experience in this area ([name], [name], [name]), based on the following samples of behavior: Connected speech samples (described below); three recorded attempts at laryngeal diadochokinesis at slow, medium, and fast rates; three trials of maximum sustained phonation; and recorded responses to the three subtests of the Apraxia Battery for Adults-2, including Speech Diadochokinesis, Repetition of Words of Increasing Length, and Word Repetition with Repeated Trials. Two judges will independently diagnose and rate the severity of motor speech disorder in each potential participant. A third judge will provide a diagnosis and rating to resolve any disagreements regarding presence or severity of motor-speech disorders. Chart review of PIRATE participants to date suggests that the above additional five criteria would have excluded approximately 20% of the unique veterans served by the program. Thus, out of 72 patients who will be seen in PIRATE over the four-year duration of the project, approximately 58 should be eligible for enrollment in the study. Of these 58 eligible veterans, it is reasonable to expect that at least 50 will enroll in the study and complete the treatment and all study visits (including follow-up visits). This sample size should be sufficient for detecting the relationships between treatment response, psycholinguistic profile, and cognitive performance relevant to Specific Aim 1, and to detect differences relevant to testing the dose-response hypotheses in Specific Aim 2.

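### The CAT mean modality T-score, one of four predicted signs of gain beyond naming in C.3.3, includes the CAT naming score, so a naming-only gain could be counted as generalized improvement

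*Combined protocol and SAP*

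**What the plan says.** C.3.3 states its purpose as evaluating "whether the study treatment is associated with broad gains in communicative function beyond confrontation naming". The CAT outcomes in its multivariate mixed model are "CAT reading, writing, auditory comprehension and mean modality T-scores", and two connected-speech measures (%CIUs and CIUs/min) complete the list. From program entry to program exit the plan anticipates "significant increases in the CAT auditory comprehension and mean modality T-scores and in the two connected speech measures", which it describes as "showing generalized improvement in communicative function". It makes no strong prediction for reading or writing.

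C.2.2 describes the CAT language battery as covering "auditory and reading comprehension, repetition, naming, spoken and written picture description, oral reading and writing". It says that T-scores are derived for eight modalities and that "a mean modality T-score is computed to provide an overall estimate of the severity of the impairment". For modality-level change, C.2.2 names only reading, writing and comprehension. C.1 confirms that naming has its own modality score, because eligibility requires that "all participants must obtain a CAT Naming modality T-score greater than or equal to 40".

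No section takes naming out of the mean, and none lists the CAT naming T-score as an outcome. C.3.3 does not say how many of the four predicted rises are needed, or how a mixed result is to be reported.

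**The concern.** SFA is a naming treatment, and C.3.3 asks whether its benefit reaches past naming. An endpoint for that question should stay still when only naming improves. The eight-modality mean does not: the treated domain is one of its components, so any naming gain passes into it, diluted.

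A significant rise in the mean therefore cannot by itself distinguish an improvement in naming from an improvement in language outside naming. The planned C.3.3 output would not show which had happened, because the CAT naming score is not among its dependent variables. Section A.2.1 calls generalization the goal that therapy is ultimately aimed at, so a claim of transfer would carry weight even though it comes from a supplementary analysis.

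**Working it through.** **No figure to reproduce.** C.3.3 gives no sample size, alpha, effect size, SD or power. The one count that can be checked is the number of modalities. The areas listed in C.2.2 are auditory comprehension, reading comprehension, repetition, naming, spoken picture description, written picture description, oral reading and writing. That makes eight, which matches the eight modalities stated there, with naming as one of them.

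**Step 1: effect of a naming-only gain.** With equal weights (inferred from the word mean), a gain of G T-points in naming and zero in the other seven gives:

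- shift in the eight-modality mean = (G + 7 × 0)/8 = G/8
- shift in the mean of the seven non-naming modalities = 0/7 = 0

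For G = 4, 6 and 8 the eight-modality mean moves by 0.50, 0.75 and 1.00 T-points.

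**Step 2: could shifts of this size reach significance?** Inputs:

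- n = 50, the completers expected in C.1.
- Two-sided alpha 0.05: assumed.
- A paired t-test on entry-to-exit change: assumed, as a simplification of the planned mixed model over four measurement points.
- G = 4, 6 and 8: assumed.
- SD of change in the mean = 1.5, 2, 3 and 4 T-points: assumed.

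The noncentrality parameter is (G/8)/(SD/√50) with 49 degrees of freedom, and the critical t is 2.01. For G = 6 and SD = 2 this is 0.75/(2/7.07) = 2.65, which gives a probability of 0.74. The full set is:

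| SD of change | G = 4 | G = 6 | G = 8 |
|---|---|---|---|
| 1.5 | 0.64 | 0.93 | >0.99 |
| 2 | 0.41 | 0.74 | 0.93 |
| 3 | 0.21 | 0.41 | 0.64 |
| 4 | 0.14 | 0.26 | 0.41 |

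**Step 3: the same result the other way round.** The naming-only gain needed for 80% power on the mean is eight times the detectable shift in the mean. At SD 1.5, 2, 3 and 4 the detectable shifts are 0.61, 0.81, 1.21 and 1.62. The required naming gains are about 4.9, 6.5, 9.7 and 12.9 T-points (computed before rounding).

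**Step 4: with the seven-modality mean.** A naming-only gain shifts the composite by zero whatever G is, so the chance of a significant result returns to alpha, 0.05 under the assumption above.

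**The case against.** The best reply is that C.3.3 does not rest generalization on the mean alone. It predicts rises in four measures, and the CAT auditory comprehension T-score, %CIUs and CIUs/min contain no CAT naming score. Reading and writing are separate dependent variables as well. A naming-only gain would appear as one diluted rise beside flat companions. This stands. A reader might infer that a naming-only gain would be reported as generalized improvement, and the documents do not support that. They support only that it could be, because nothing says what follows if the mean rises alone.

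A reader might also take the tabled probabilities as an inflated false-positive rate. They are not. If naming rises, the eight-modality mean truly rises, and rejecting no change in that mean is correct. The error would lie in reading the rise as transfer.

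The size is also open to challenge. The documents give neither an expected CAT naming gain nor an SD of change, and the answer moves widely with both. This stands too, and the table shows sensitivity only. The overlap itself does not depend on those inputs.

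Section B.1.2 notes that the PICA mixes treated and untreated domains. Its point is that a broad index understates treatment effects, so it should not be read as an admission that such an index overstates transfer. It does show that the sponsor recognises the mixing.

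Finally, the mean modality T-score is the standard CAT summary. A seven-modality version is not, and its picture-description components may still draw on word retrieval. These are fair costs. They argue for keeping the standard score in its severity role, but they do not make it a measure of gain beyond naming.

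**Conclusion.** The point holds as a limited flaw of interpretation. One of four predicted signs of generalized improvement contains the domain it is meant to look beyond. The overlap follows from C.1, C.2.2 and C.3.3 read together, and the G/8 shift adds only the inference of equal weighting. How often it would matter cannot be fixed from the documents. Under the assumed inputs, the chance that a naming-only gain makes the mean significant runs from 0.14 (G = 4, SD 4) to above 0.99 (G = 8, SD 1.5).

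The three companion measures limit the risk. The missing rule for a mixed result and the absence of a separate CAT naming analysis leave it open. C.3.3 is supplementary: the Aim 1 outcomes (treated probes, with untreated related probes and the PNT as secondary) and the Aim 2 dose-response analyses do not use the CAT mean as an outcome.

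**What to change.** In C.3.3:

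- Base the inference about gains beyond naming on the mean of the seven non-naming CAT modality T-scores, computed from the same administrations.
- Report the CAT naming T-score separately, as the standardized CAT measure of the treated domain.
- Keep the eight-modality mean as the overall severity summary, and state that a rise in it is not read as evidence of transfer.
- State in advance which of the predicted measures must rise before generalization is claimed, and how a mixed result will be described.

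The cost is a few lines of text, with no new data or visits. The expected effect on the composite will be smaller, the composite is not the standard CAT summary, and the picture-description modalities may still carry some word-retrieval benefit. The last two limits should be acknowledged when the result is reported.
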